1c. Swelling	Is/was there any swelling either outside the hard woody lump or without any hard lump in the middle?								
	No swelling — go to next question	0							
	Yes, take measurement (measure tool used  OR estimate )	1	
 
 >0.0 – <1.0cm	2	
 
 =>1.0 – <2.5cm	3	
 
 =>2.5 – <5.0cm	4	
 
 =>5.0 – <10.0cm	5	
 
 =>10.0 – <15.0cm	6	
 
 =>15.0 – <20.0cm	7	
 
 =>20.0 – <30.0cm	8	
 
 =>30.0cm	9	
 
  1d. Pain intensity	Is/was there any pain where the injection was given?							
	No pain — go to next question	0							
	Yes, to what extent	1							
	• Mild, still able to move arm normally	2							
	• Moderate, hurts to move arm normally or to touch	3							
	• Severe, unable to move arm	4							
	1e. Interval and duration for onset of local event or first observation	Where applicable, how long after having the vaccination did the event occur? Circle as appropriate. How long did the event last?							
		Redness	Duratio n	Induratio n	Duratio n	Swelling	Duratio n	Pain	Durati on
		>0 – 24hrs	>0 – 24hrs	>0 – 24hrs	>0 – 24hrs	>0 – 24hrs	>0 – 24hrs	>0 – 24hrs	>0 – 24hrs
24 – 48hrs		24 – 48hrs	24 – 48hrs	24 – 48hrs	24 – 48hrs	24 – 48hrs	24 – 48hrs	24 – 48hrs	
49 – 72hrs		49 – 72hrs	49 – 72hrs	49 – 72hrs	49 – 72hrs	49 – 72hrs	49 – 72hrs	49 – 72hrs	
73hrs – 7 days		73hrs – 7 days	73hrs – 7 days	73hrs – 7 days	73hrs – 7 days	73hrs – 7 days	73hrs – 7 days	73hrs – 7 days	
>7 days			>7 days		>7 days		>7 days		

1. Did you feel feverish after you received the vaccine?		
	No fever — go to question 2c	0
	Yes, had fever	1
2a.	How long after the vaccine did the fever occur?	
	0–4 hrs	1
	5–8 hrs	2
	9–24 hrs	3
	or after 24 hrs?	4
2b.	Was the temperature measured?	
	Temperature not taken	0
	Temperature taken but don't know what it was	1
	Temperature taken and read as below:	
	<38°C	2
	38.0–38.4°C	3
	38.5–38.9°C	4
	39.0–39.4°C	5
	39.5–39.9°C	6
	40.0–40.4°C	7
40.5–41.0°C	8	
2c.	Was anti-fever/pain medicine given or did you take anti-fever/pain medicine? (e.g., panadol/nurofen)	
	No meds given/taken — go to question 3	0
	Yes, meds given/taken	1
	Don't recall	88
2d.	Was it given/taken before or after vaccination?	
	Before	1
	After	2
	Both	3
	Don't recall	88

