2. Did you have any other symptoms after you received the vaccine?		

No — go to question 4	0
Yes — circle below as appropriate	1
Events	
Nausea, vomiting or diarrhoea	1
Headache	2
Fatigue, lethargy or general weakness	3
Events around the area where you got the injection (other than those already discussed)	4
Pain (including muscle or joint pain: not injection site pain)	5
Intense shivering/Shaking	6
Other (details)	7
3. Did you need to see or call the doctor for any reason in the 24–48 hours after having the vaccine?	
No, did not need to contact the doctor — go to question 5	0
Yes, did need to contact the doctor	1
Who did you see?	
Where?	
For what reason?	
Can we contact your doctor for more information?	Yes / No
4. Other than the vaccine you just had, have you received the Tdap (Boostrix®) vaccine (whooping cough) previously?	
No, not had Tdap before — go to end	0
Yes, had Tdap before (may need prompt, eg, if they have had tetanus in recent years)	1
Don't know — go to end	88
Can you remember which brand it was? What brand was it?	Yes / No

Ethical approval

APPROVED BY THE UNIVERSITY OF AUCKLAND HUMAN PARTICIPANT ETHICS
COMMITTEE ON **/**/** for *** years. Ref No ****/**.

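### Study Two Phone Survey 1 prints its main questions as 1–4 while its sub-items and skips fit 2–5, so followed as printed some women are never asked about systemic symptoms or early doctor contact

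*Protocol*

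**What the plan says.** Under Study procedures, the Protocol makes the first phone contact the source of early solicited events in Study Two. The Study Two endpoint is the rates and patterns of adverse events in vaccinated women. These are to be reported as percentages with 95% confidence intervals in about 300 women.

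The form for that call is Appendix 6. After the local-reaction items 1a–1e it runs as follows.

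- Fever: "1. Did you feel feverish after you received the vaccine". Its sub-items are labelled 2a to 2d, and its own exit is "No fever — go to question 2c".
- Item 2c, use of fever or pain medicine: the exit for women who took none is "No meds given/taken — go to question 3". Those who answer Yes or cannot recall have no skip.
- Systemic symptoms: "2. Did you have any other symptoms after you received the vaccine", with a list covering gastrointestinal symptoms, headache, fatigue, other pain and shivering. The exit for women with none is "No — go to question 4".
- Doctor contact, printed as question 3: "Did you need to see or call the doctor for any reason in the 24–48 hours after having the vaccine". The exit is "No, did not need to contact the doctor — go to question 5".
- Previous Tdap, printed as question 4. No question 5 is printed.

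**The concern.** The skip instructions and the printed question numbers cannot both be right. Two of the three faulty skips land on a real question, so an interviewer who follows them gets no signal that anything was missed. Only the third, to question 5, reveals itself.

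The first skip makes the systemic-symptom list conditional on medicine use, which is likely to be related to having symptoms. Whether a woman is asked would then depend on something tied to the answer, and the early systemic-event percentages would not describe the 300 women. An answer that was never solicited cannot be recovered at analysis.

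Comparability is also affected. The Protocol says that Study Two data will be directly comparable with the Canterbury data (Study Three) and can be analysed jointly for maternal outcomes. The data items listed for the Canterbury women (Appendix 8) cover the same kinds of reaction and doctor contact, and show no skips.

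**Working it through.** **Tracing the skips.** Each onward skip is followed on the printed numbers, then with the four questions numbered 2, 3, 4 and 5.

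| Exit | Skip target | As printed, lands on | Passed over | If numbered 2–5, lands on |
|---|---|---|---|---|
| Fever, No | 2c | medicine item | 2a, 2b (intended) | same |
| 2c, none taken | 3 | doctor contact | systemic symptoms | systemic symptoms |
| Systemic symptoms, No | 4 | previous Tdap | doctor contact | doctor contact |
| Doctor contact, No | 5 | nothing | undefined | previous Tdap |

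All three onward numbered skips are off by exactly one. The skip to 2c resolves only because it points to a sub-item label, and that label shows that the fever question was meant to be number 2. Numbered 2 to 5, every skip resolves and no main question is bypassed.

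**Who is affected under literal routing.**

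- No medicine taken: not asked the systemic list; asked about doctor contact.
- Medicine taken, or not recalled: asked the systemic list. Those who answer No to it are not asked about doctor contact.
- Fever and local reactions come before the faulty skips and are asked of everyone.

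**What Survey 2 (Appendix 7) covers.** At four weeks every woman is asked about any adverse event or symptom, infections, muscle aches, severe nausea or vomiting, and whether she needed a doctor for any reason since vaccination. Headache, fatigue, shivering and milder gastrointestinal symptoms are not listed. These are the items left exposed.

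**Illustration of size.** The Protocol gives none of these inputs, so all are assumptions: share reaching the systemic list *m* = 0.20 to 0.40; true symptom proportion *p* = 0.30; symptom risk in those reaching the list relative to the others *R* = 1 to 2.

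Women asked: 300 × 0.20 = 60 to 300 × 0.40 = 120.

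Proportion among those asked: *q* = *Rp* / (1 + *m*(*R* − 1)).

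- *R* = 1: *q* = 0.30.
- *R* = 2, *m* = 0.20: 0.60/1.20 = 0.50.
- *R* = 2, *m* = 0.40: 0.60/1.40 = 0.43.

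If blanks are treated as missing, the reported figure is *q*: 30% to 50% against a true 30%.

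If blanks are read as No, the reported figure is *m* × *q*: from 0.20 × 0.30 = 0.06 to 0.40 × 0.43 = 0.17.

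Precision also falls. With *R* = 1 and blanks missing, the 95% half-width is 1.96 × √(0.30 × 0.70/*n*): 0.052 at *n* = 300, 0.082 at 120 and 0.116 at 60.

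**The case against.** Four arguments weigh against the point.

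- **Text extraction.** The text at hand was read from a PDF by a program, and the tables in this appendix show conversion damage. A numbered list that lost its start value would produce this pattern, so the printed form must be checked. The contradiction stands in the text as read.
- **Obvious intent.** The survey is given by a research-team member who is told to probe for symptoms. Two questions numbered 1 and a skip to a missing question 5 would probably expose the slip early. This lowers the expected harm. If some interviewers follow the skips and others do not, however, missingness depends on the interviewer.
- **Survey 2.** It gives every woman a second chance to report doctor visits and general events, and the Protocol has the practice verify events that needed a consultation. This stands, and it limits the loss to the symptoms that Survey 2 does not name.
- **Coding of blanks.** A reader might infer that unasked items count as no event, so that systemic proportions are biased downward, for example 6–17% in place of 30%. The Protocol does not support that. The form has an explicit code 0 for No, so an unasked item is a blank, and nothing says that blanks become 0. Left missing, they give no bias or an upward one.

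A reader might also infer that every woman without other symptoms misses the doctor question, or that medically attended events are lost to Study Two. Neither follows. Women who took no medicine go straight to the doctor question, and Survey 2 asks everyone about doctor visits.

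**Conclusion.** The numbering in Appendix 6 contradicts itself and should be corrected. As printed, the systemic-symptom list goes only to women who took medicine or could not recall, and those among them who answer No are not asked about early doctor contact.

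What is at risk is the early percentage for headache, fatigue, shivering and milder gastrointestinal symptoms. It would be selectively missing, and the direction of bias depends on how blanks are handled. In the illustration a true 30% reads as 30–50% with blanks missing and as 6–17% with blanks read as No. These are outer cases. They need every interviewer to follow the skips literally, and they rest on assumed rates of medicine use and symptoms.

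The conclusion also assumes that the printed form carries the numbers as read here. Only the Protocol was at hand; a statistical analysis plan could set the rule for blanks but could not restore unasked answers.

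**What to change.** Check the numbers on the form in use. If they are as read here, renumber the four main questions after the local-reaction block as 2, 3, 4 and 5. Every skip then resolves, and every woman is asked the systemic-symptom and doctor-contact items. Changing only the skip targets is less tidy, because 2a–2d would still sit under a question numbered 1.

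For interviews already done on the misnumbered form, code skipped items as missing and not as No, and report the number of women actually asked as the denominator for each item.

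The cost is four numerals, a new form version and a word to the interviewers. The call is no longer than intended.

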- Estimated minimum and maximum number of women for follow up of pertussis vaccine 1,527–20,358

Sample size and power

As this is an observational study we plan to describe the confidence intervals for the proportions of AEs. With a sample of 300 vaccinated participants, if event occurs in 10% of the group the 95% CI would be 7–14%; if 5%, 2.8–8.1%; if 1%, 0.2–2.9%. Additional power will be achieved by combining the data from the Canterbury study (Study Three), which aims to include 300 women vaccinated with Tdap.

Statistical Analyses

The pregnancy safety data will be descriptive in nature, including percentages and 95% confidence intervals. The rates of AEs and SAEs following pertussis vaccine will be discussed in context with the rates previously described for pertussis. The expected background rates of MAEs and SAEs for Tdap given during pregnancy are unknown, but as a guide the rates of MAEs for pregnant women receiving influenza vaccine previously reported ranged from 1.1 to 3.8% while the rate of SAEs ranged from 0.4 to 1.5%.

Women who have complicated pregnancies will be excluded from the final analyses and described separately.

The temporal relationship between onset of events and vaccination will be presented including distribution where appropriate.

Serious adverse events will be reported as detailed clinical cases. Other events will be groups according to Brighton Collaboration Definitions.

Study Three (N=~300)

From the protocol for Canterbury DHB (Appendix 8): Principal Investigator, [name].

As this study is an observational study, the pregnancy outcomes and safety data will be descriptive in nature. The rates of AEs and SAEs will be compared to published background rates for the general population. The expected rates of MAEs and SAEs for Tdap given during pregnancy is unknown, but as a guide the rates of MAEs for pregnant women receiving influenza vaccine in this paper ranged from 1.1 to 3.8% while the rate of SAEs ranged from 0.4 to 1.5%. Where the known background incidence of 0.01 for a particular adverse event, a sample size of 300 achieves 80% power to detect an additional incidence rate of 0.0175 when the significance level is 0.05.

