
Level one diagnostic certainty is: Any description of morphological or physiological change at or near the injection site that is described or identified by a health care provider
 
Level two diagnostic certainty is: Any description of morphological or physiological change at or near the injection site that is described or identified by another person
 
Categories for event classification
 
Level 1: as specified in the case definition for a local reaction
 
Level 2: as specified in the case definition for local reaction
 
Insufficient evidence for a local reaction Not a case of a local reaction
 
Interval for onset of local reaction or first observation
 
>0-24 h 25-48 h 49-72h 73h – 7 days >7 days
 
Include numbers of subjects with local reactions newly present at each specified time as %.
 
Diameter of the local reaction
 
>0.0 - <1.0 cm ≥1.0 – 2.5 cm
	
Fever
 
Endogenous elevation of at least one measured body temperature of ≥38°C
 
Time intervals
 
0 – 24hr Day 1 0 – 24hr Day 2 Day 3-7...
 
Increments
 
<38°C 38.0-38.4°C 38.5-38.9°C Etc.... >41°C

≥2.5 – 5.0 cm ≥5.0 - <10.0 cm ≥10.0 - <15.0 cm ≥15.0 - <20.0cm ≥20.0 - <30.0 cm ≥30.0 cm
 
Pain scale to include measure of functionality
 
0 = No pain 1 = Mild, still able to move arm normally 2 = Moderate, hurts to move arm normally or to touch 3 = Severe, unable to move arm
	
--	--

Ethical considerations

Ethical approval for this study will be obtained from the NZ Ministry of Health and Disability Ethics Committee. These guidelines are based on statements from NZ and international guidelines, including the World Medical Association Declaration of Helsinki: Ethical principles for medical research involving human subjects (WMA 2008) and the Council for International Organizations of Medical Sciences' International Guidelines for Ethical Review of Epidemiological Studies (CIOMS 1991).

Details about the National Ethics Advisory Committee and the Ethical Guidelines for Observational Studies can be accessed <http://neac.health.govt.nz/streamlined-ethical-guidelines-health-and-disability-research>

Whilst we are not undertaking any clinical work (there is no intervention, only observation), we will be observing the standards required by the national ethics committee and GCP standards, in which our team are familiar.

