Appendix 6: Study Two Phone Survey 1 (48hrs–7days post vaccine)

[name]
 Department of General Practice & Primary Health
 SCHOOL OF POPULATION HEALTH
 The University of Auckland
 [name]
 Auckland, 1142
 [contact]

PIPS Study Patient Participant Phone Interview 1 (48 hours–7days post vaccine)

The following questions ask about your memory of events for the period immediately (within 48 hours) following when you received the dose of Tdap vaccine (whooping cough vaccine).

Since having the vaccine, have you experienced any of the following at the place on your arm where you had the injection?

[Tease out potential symptoms and events related to vaccination eg, distinguish between what may be related to pre/post-pregnancy, “is this more than usual?”]

If you have had any redness or swelling, use the clear plastic measure the practice nurse gave you.

Use the smallest circle you can use to cover all of the redness or swelling, and this will give you the measurement of the reaction. If the reaction is bigger than the biggest circle, use the ruler down the side.

Event	Description/Question	Grade/Response	
1a. Redness	Has there been any redness where the injection was given?		
	No redness — go to next question	0	
	Yes, take measurement (measure tool used  OR estimate )	1	
 
 >0.0 – <1.0cm	2	
 
 =>1.0 – <2.5cm	3	
 
 =>2.5 – <5.0cm	4	
 
 =>5.0 – <10.0cm	5	
 
 =>10.0 – <15.0cm	6	
 
 =>15.0 – <20.0cm	7	
 
 =>20.0 – <30.0cm	8	
 
 =>30.0cm	9	
 
  1b. Induration	Is/was there a hard, woody lump with defined edges, where the injection was given?	
	No induration — go to next question	0	
	Yes, take measurement (measure tool used  OR estimate )	1	
  
 
 
 
© Immunisation Advisory Centre, The University of Auckland_V2_29/10/2013
		

	>0.0 – <1.0cm	2							
	=>1.0 – <2.5cm	3							
	=>2.5 – <5.0cm	4							
	=>5.0 – <10.0cm	5							
	=>10.0 – <15.0cm	6							
	=>15.0 – <20.0cm	7							
	=>20.0 – <30.0cm	8							
	=>30.0cm	9							

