Date of Birth (of the woman)	
Ethnicity i.e. Maori/Pacific Island/NZ European/ Other.....	
Estimated due date (used to work out gestational age)	
Date of vaccine administration	

Arm which vaccine(s) were given in	
Vaccine product name and batch number	
Any immediate (within 30 minutes) side effects?	
Any other observations?	
Concomitant vaccines administered	
Previous pertussis booster given	
History of fever or vaccination reaction	
Health and underlying medical condition	
Inclusion Criteria:	
Received Tdap after 30 weeks gestation	Yes/No
Compliant with routine antenatal care, including at least 1 ultrasound early in pregnancy	Yes/No
Exclusion criteria:	
Receipt of Tdap (pertussis) vaccination before 30 weeks	Yes/No

Study Title: Safety Monitoring of Adverse Reactions to Tdap Vaccine in Pregnancy

The woman will be asked to provide data that will include the following for the period immediately following each dose of Tdap or influenza vaccine is received:

- Did she have any symptoms immediately after receiving the vaccination? (Yes/No)
later same day next day lasted-
- Was there any local reaction in the arm where the vaccination was given? (Yes/No)
or see below for details of classification
- Recall of fever (Yes/No) if yes what time frame did the fever – see below for details of classification
- Was the temperature measured? (Yes/No) if yes what was the measured temperature? – see below for details of classification
- Was there any other reactions
 - Nausea, vomiting or diarrhoea
 - Headache
 - Fatigue, lethargy or general weakness
 - Injection site reactions
 - Pain (including muscle or joint pain: not injection site pain)
 - Rigors/Shaking
 - Other (details)
- Was anti-fever medicine given (Yes/No) if yes was it given before or after vaccination?
- Did you need to call or see a doctor? (Yes/No) if yes who, where and why
- Had she received the Tdap vaccine previously? (Yes/No) if yes can she remember which brand it was?
- Can we contact them for more information (Yes/No)

All as per Brighton Collaboration where these definitions are available.^{2 3}

Definitions for local reactions and fever	
Local Reactions	Systemic Events

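### Survey 1 has no onset or duration field for non-fever systemic symptoms and Survey 2 only partly fills the gap, so Study Two's planned presentation of onset relative to vaccination would be incomplete

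*Protocol*

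**What the plan says.** The Study Two statistical analyses section states: "The temporal relationship between onset of events and vaccination will be presented including distribution where appropriate". The analysis is otherwise descriptive, with percentages and 95% confidence intervals in about 300 vaccinated women.

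Survey 1 (Appendix 6) collects timing in two places. Item 1e covers redness, induration, swelling and pain. It asks "Where applicable, how long after having the vaccination did the event occur" and then how long the event lasted, both in bands. Item 2a asks "How long after the vaccine did the fever occur" and offers four bands.

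The following block asks "2. Did you have any other symptoms after you received the vaccine". After a yes, the interviewer circles codes such as "Fatigue, lethargy or general weakness". No field for onset or duration follows.

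On the period covered, the survey's title gives 48 hours to 7 days, while its introduction reads "The following questions ask about your memory of events for the period immediately (within 48 hours) following when you received the dose of Tdap vaccine".

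Survey 2 (Appendix 7), at four weeks, has columns for the date an event started and the date it resolved. Its rows are a general question on any adverse event or symptom in the month, a row on infections, and a list of named events.

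**The concern.** A promised presentation depends on a data item that the form does not collect for most systemic symptoms. The protocol itself fixes the form, so a later analysis plan cannot supply an onset that was never asked.

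The symptoms are not marginal. The Canterbury protocol's section on related research lists fatigue, gastrointestinal symptoms, headache, joint pain, muscle aches and shivering, together with fever, as the solicited general symptoms in earlier work on this vaccine.

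Study Two enrols vaccinated women only. The form acknowledges that pregnancy symptoms may be mixed in, because it tells the interviewer to probe whether a complaint is more than usual. That prompt stands with the injection-site questions and has no answer field. A bare proportion of women with headache or fatigue then gives little indication of whether reports gather in the first days or are spread over the period.

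**Working it through.** No arithmetic decides this point. The check is to follow each type of event through the two surveys.

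**Survey 1 (Appendix 6)**
- Redness, induration, swelling, pain: onset yes, duration yes (item 1e).
- Fever: onset yes (item 2a), no duration field.
- Other-symptoms block: seven codes. One covers further events around the injection site; the other six are systemic or unspecified. Onset no, duration no, for all seven.

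**Survey 2 (Appendix 7), for the six systemic codes**
- Nausea, vomiting or diarrhoea: dated only in part. There is a row for severe nausea or vomiting, and gastroenteritis is an example in the infections row. Non-severe nausea and diarrhoea outside an infection have no row.
- Headache: no named row.
- Fatigue, lethargy or weakness: no named row.
- Muscle or joint pain: muscle aches have a dated row; joint pain has none.
- Shivering: no named row.
- Other: no named row.

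Three of the five named systemic codes (headache, fatigue, shivering) thus have no dated row of their own in either survey, and two are covered in part.

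**The catch-all row.** It can take a start date for anything a woman mentions. As printed it holds one date and no field naming the symptom. The question on signs and symptoms comes only after a doctor visit; a woman who saw no doctor is sent to the end. Someone with a headache on day 1 and fatigue on day 10 who saw no doctor would leave one date, recalled at four weeks and linked to neither symptom.

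**The recall window.** If Survey 1 covered exactly 48 hours, a circled code would at least place onset within two days. The introduction says that, but the title runs to 7 days, the Study Two enrolment procedures ask for events in both the first 48 hours and the first 7 days, and a footnote there allows women to be contacted retrospectively. A circled code therefore does not fix the onset.

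**The protocol's own figures.** The only Study Two precision figures are the 95% intervals for n = 300. Exact Clopper-Pearson limits reproduce them: 30/300 gives 6.9–14.0% (stated 7–14%), 15/300 gives 2.8–8.1%, and 3/300 gives 0.2–2.9%. These concern how many women report an event, not when it began, and the point does not depend on them.

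**The case against.** The planned presentation carries the qualifier on appropriateness, promises no list of systemic symptoms or time bins, and sits in a descriptive study that makes no causality assessment. That is true and limits how firm the commitment is. It does not explain why mild redness is timed on the same call and headache is not.

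Four stronger readings are tempting, and the documents do not support them.

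- A reader might infer that no systemic event is timed. Fever, defined as "Endogenous elevation of at least one measured body temperature of ≥38°C", is the one event the protocol lists under systemic events, and its onset is recorded.
- A reader might infer that the onset presentation cannot be done at all. Survey 2 dates muscle aches, severe nausea or vomiting, and whatever reaches the catch-all row. The presentation is incomplete, not impossible.
- A reader might infer that the systemic proportions cannot be interpreted, or that onset would separate reactions from pregnancy symptoms. The protocol also plans to set rates beside those described previously, and the interviewer prompt is a weak safeguard. Early clustering in uncontrolled, unblinded recall can itself be a reporting effect.
- A reader might infer that Canterbury collects what Study Two omits. Its timing prompt, "later same day next day lasted", belongs to a question about symptoms immediately after vaccination. Its matching list of other reactions also has no onset for each symptom.

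**Conclusion.** The point holds in limited form. Survey 1 times none of the six non-fever systemic codes. Survey 2 recovers start dates for muscle aches and severe nausea or vomiting, and otherwise offers one date recalled at four weeks and not tied to a named symptom. The onset presentation planned for Study Two would be incomplete for headache, fatigue, shivering, diarrhoea, joint pain and non-severe nausea.

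No numerical size can be given: the protocol states neither background rates nor expected frequencies for these symptoms in Study Two, and the Survey 1 window is itself unsettled. The stated intervals for proportions are unaffected.

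The conclusion assumes that the surveys as printed are the complete forms and that interviewers record nothing outside the printed fields. It is a worthwhile correction to make before interviews start, because onset not asked then could be sought later only by longer recall. It does not invalidate Study Two.

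**What to change.** - Add the item 1e onset and duration bands to each circled code in the Survey 1 other-symptoms block, recorded per symptom.
- State one recall window for Survey 1 and use it in the title, the introduction and the study procedures.
- Present onset for these symptoms in the same way as for local reactions.

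The bands and the phone call already exist. The cost is extra columns on the form and about a minute more per symptomatic woman. Two limits remain. The onset data would still be subject to recall and reporting bias. Because the Canterbury list has no onset for each symptom either, this information would come from Study Two alone in any pooled maternal analysis, unless that form is changed as well.
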